3.3 Interventions

Paramedics will be trained in the use of the CCR prior to the start of the trial. We have conducted an Ottawa EMS CCR implementation pilot study and have designed our training program to address barriers identified in the pilot. The training entails one hour of education: 30 minutes of self-review of a teaching video addressing the background and scientific development of the CCR, and a 30-minute inclass teaching video reviewing the specific steps involved in using the CCR, complete with a demonstration and question and answer period with a certified trainer. Paramedics will be "certified" to clear the cervical spine by medical directive if they have: a) successfully completed the initial training sessions, and b) successfully completed (score of ≥80%) a written quiz. Paramedics failing the written quiz would be required to attend a remedial session and review all wrong answers with their certified trainer. Of note, Ottawa paramedics all successfully completed their training.

The stepped wedge trial will begin after paramedic training has been completed (see Figure 2). During the Usual Care phase, paramedics will complete the CCR data collection form for all eligible patients, but will continue to immobilize them all before transport to the receiving hospital. Once a community has crossed to the intervention CCR phase, paramedics will be permitted by medical directive to implement the CCR. Paramedics will then transport selected patients without immobilization according to the CCR. Although following the medical directive will be mandatory for paramedics, they will be encouraged and allowed to immobilize patients if they are uncomfortable with the CCR's recommendation to not immobilize them.

During the study set-up time period (Figure 2), each participating service will designate a local paramedic study champion. These individuals will be in close contact with staff at the Study Coordinating Centre and will receive further information about the study, the methodology and the implementation of the CCR. These individuals will be heavily involved in delivering the study training material at their particular location and will serve as a first point of contact throughout the implementation. Paramedics with questions about specific aspects of the CCR, or the application of the CCR for unusual scenarios will be able to communicate directly with a peer in an effort to promote adherence to the protocol.

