3.6 Sample Size

Our sample size for this study is determined mainly by pragmatic considerations: we need a large number of sites from across Ontario to evaluate safety and generalizability of implementation in this multicenter setting, while accounting for between-site differences such as size and setting. Power calculations were carried out for the stepped wedge trial. Using data from a previous study in these communities, we expect approximately 600 patients per EMS service per year (or 150 patients per 3 month time interval). A total of 12 EMS services (7,200 patients) evaluated across 4 time intervals in a stepped wedge design will provide at least 90% power to detect minimally important differences of 10% in our two co-primary outcomes using two-sided tests at the 2.5% level of significance. In particular, for our primary outcome we will have >99.9% power to detect a minimally important absolute reduction of 10% in the proportion of patients immobilized assuming a control arm proportion of 100%. For our co-primary outcome we will have 90% power to detect a minimally important increase of 10% in the proportion of patients feeling comfortable assuming a conservative control arm proportion of 50%. In these calculations, we have assumed a commonly used intracluster correlation coefficient (ICC) of 0.05, added 2 EMS services to account for variation in the number of patients across sites, and a further 2 EMS services to account for potential attrition.

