5.4 Statistical Methods

Analyses will be conducted at the level of individual patient data using generalized linear mixed effects regression with a random effect to account for clustering by EMS service, and fixed effects for treatment and time interval to account for the stepped wedge design. The primary and co-primary outcomes will be analyzed using binomial distribution with identity link and the effect of intervention will be expressed as absolute differences with 97.5% confidence intervals. Secondary outcomes will be similarly analyzed using binomial distribution and identity or logit link for dichotomous variables, normal distribution and identity link after log-transformation or gamma distribution and log-link for continuous variables with a skewed distribution, or Poisson or negative binomial distribution with log link for count variables. The effect of the intervention on each secondary outcome will be described using absolute difference, Relative Risk or Odds Ratio with 95% confidence interval. Subgroup analyses (described below) will be conducted by including interactions with time interval and treatment in the regression model.

Our **health economist** will perform a cost-effectiveness analysis from the perspective of the Ministry of Health and Long-Term Care. Trial data will be used to populate the relative costs and outcomes of the use of the CCR by paramedics with usual care (100% immobilization). Resource use will be collected during the trial and obtained from ICES, while unit costs will be obtained from appropriate Canadian

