sources, such as Schedule of Benefits for Physician Services. Total cost for each patient includes costs of the intervention and costs of health services, including the follow-up period of 30-days post ED discharge. Cost of intervention covers cost of training and operation. Costs of operating paramedic services include personnel cost (e.g. salaries and employee benefits), service cost (e.g. fuel, maintenance), medical supplies (e.g. an on-board liquid oxygen system, medications, and single-use patient care supplies). Costs of healthcare services will be obtained from ICES and will be estimated by multiplying the unit costs by the volume of healthcare used. We will use mixed-effects regression analyses to estimate the difference in expected healthcare costs and outcomes between the intervention and control groups. The incremental cost-effectiveness ratio will be estimated by dividing a difference in cost by a difference in the number of immobilizations. The 95% confidence interval will be calculated using a non-parametric bootstrapping method. Results from the bootstrapping exercise will also be used to depict a cost-effectiveness acceptability curve (CEAC), which links the probability of a treatment being cost-effective to a range of potential threshold values (λ) that the health system may be willing to pay for an additional unit of effect (17). A CEAC is a graphical representation of the probability that the CCR may be cost effective given alternate dollar values placed on an outcome. This will allow estimation of the probability that the CCR can be considered cost-effective given the available data. In addition, sensitivity analysis will be undertaken to examine the effect of conducting a complete caseonly analysis and of varying the cost of the intervention.

We will also conduct a budget impact analysis to estimate the financial consequences of implementing the CCR by paramedics in Ontario. All analyses will be conducted using STATA version 13.0 and Microsoft Excel and Visual Basic for Applications.

Pre-Specified Sub-Group Analyses will be conducted to examine the differential effects (possible inequity) of the intervention on the following groups, defined by:

- a) sex
- b) language barrier present vs. not (collected by paramedics on data collection form),
- c) long transport times (longer vs. shorter than 15 min),
- d) age (adult ≥16 vs. children <16),
- e) socioeconomic status and education level (ICES data), and

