Appendix 5. Patient Committee Terms of Reference To be appended once developed and finalized.

Appendix 6. Paramedic Data Collection Form

EVALUATION OF THE SAFETY OF C-SPINE CLEARANCE BY PARAMEDICS CALL NUMBER: DATE OF CALL (YY/MM/DD): 1. INCLUSION CRITERIA (check as applicable) ALERT (GCS 15) STABLE (SBP ≥90mmHg, respiratory rate 10-24/minute) **ACUTE BLUNT INJURY (<48 hours)** Are all the inclusion criteria met? ■ NO - STOP; can't use the Canadian C-Spine Rule 2. EXCLUSION CRITERIA (check as applicable) Boarded and collared for reason other than c-spine injury Age < 8 years Penetrating trauma from stabbing or gunshot wound Acute paralysis (paraplegia, quadriplegia) Known vertebral disease (ankylosing spondylitis, rheumatoid arthritis, spinal stenosis, previous c-spine surgery) Referred from another hospital Does the patient have any exclusion criteria? ☐ YES - STOP: can't use the Canadian C-Spine Rule ■ NO - CONTINUE 3. THE CANADIAN C-SPINE RULE START HERE 1. Any ONE high-risk factor which mandates immobilization? ☐ No ☐ Yes Age ≥65 years ☐ No ☐ Yes Dangerous Mechanism* ☐ No ☐ Yes Numbness or tingling in extremities ☐ YES - STOP ■ NO - CONTINUE 2. Any ONE **low-risk** factor which allows safe assessment of range of motion? ☐ No ☐ Yes Rearended in Simple Rearend MVC** ■ NO - STOP ☐ No ☐ Yes Ambulatory at any time at scene ☐ C-SPINE IMMOBILIZATION ☐ No ☐ Yes No neck pain at scene when asked (answer "yes" if no pain) ☐ No ☐ Yes No pain during midline c-spine palpation (answer "yes" if no pain) Dangerous Mechanism: -fall from elevation ≥3 feet/5 stairs □ NO ☐ YES - CONTINUE axial load to head, e.g. diving -MVC: rollover, ejection, high speed (≥100km/h) -motorized recreational vehicles, e.g. ATV, 3. Patient voluntarily able to actively rotate neck 45° left and right when snowmobile requested, regardless of pain? -bicycle collision with object, e.g. post, car ☐ No ☐ Yes **Simple Rearend MVC Excludes: -pushed into oncoming traffic ☐ YES -hit by bus/large truck -rollover ■ NO C-SPINE IMMOBILIZATION -hit by high speed vehicle (≥100km/h) 1. According to the Canadian C-Spine Rule, would this patient require immobilization? 2. How comfortable would you be in following the Canadian C-Spine Rule for this patient? very comfortable ☐ comfortable ☐ neutral □ uncomfortable very uncomfortable 3. If you were uncomfortable, please briefly describe why: 4. Will you use the Canadian C-Spine Rule when deciding whether or not to immobilize this patient? Yes, this patient will be transported with or without immobilization according to the Canadian C-Spine Rule. ☐ No, I am choosing to immobilize this patient, despite the rule indicating immobilization is not required. 5. Was there a language barrier present that hindered your ability to apply the Canadian C-Spine Rule to this patient? 🗖 No 🗖 Yes 6. Before transfer of care to the Emergency Department, please ask your patient the following questions: i) On a scale of 1 – 10 (10 being the highest level of pain), how would you rate your pain right now? ii) On a scale of 1-10 (10 being very uncomfortable), how would you rate your comfort level right now?

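### The language-barrier subgroup cannot be built from the form, which records only barriers judged to have hindered use of the rule

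*Combined protocol and SAP*

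**What the plan says.** Section 5.4 states that subgroup analyses "will be conducted to examine the differential effects (possible inequity) of the intervention on the following groups". The second group on its list is "language barrier present vs. not (collected by paramedics on data collection form". The method is also given there: subgroup analyses "will be conducted by including interactions with time interval and treatment in the regression model". Section 2.2 lists measuring health inequities in prehospital care among the project's wider aims.

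The form in Appendix 6 has one language question, item 5: "Was there a language barrier present that hindered your ability to apply the Canadian C-Spine Rule to this patient". It is answered No or Yes. It comes after the questions on the rule's result (item 1), the paramedic's comfort with following it (item 2) and the decision to act on it (item 4: "Will you use the Canadian C-Spine Rule when deciding whether or not to immobilize this patient").

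The form is used in both conditions. Section 3.3 says: "During the Usual Care phase, paramedics will complete the CCR data collection form for all eligible patients". Once a service has crossed over, paramedics may depart from the rule in one direction: "they will be encouraged and allowed to immobilize patients if they are uncomfortable with the CCR's recommendation to not immobilize them".

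**The concern.** The planned subgroup is a patient characteristic: is there a language barrier or not? The recorded item is a joint condition: a barrier was present and, in the paramedic's judgement, it got in the way of the rule. The two agree only if every barrier hinders.

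The narrower item is tied to delivery of the intervention. Several steps of the rule rest on communication: reported numbness or tingling, neck pain when asked, and neck rotation on request. A patient who does not rotate the neck is immobilized under the form, and an uneasy paramedic may immobilize in any case. Patients marked as hindered are thus likely to be immobilized more often in the intervention phase. Patients whose barrier was handled well drop out of the subgroup. A low effect in the Yes group could then be read as inequity towards all language-barrier patients, which the data would not show.

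**Working it through.** The plan states no figure on this point, so there is none to reproduce. The check is a comparison of definitions, followed by an illustration of size.

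**Step 1. Can the planned variable be obtained elsewhere?**
- Appendix 6: item 5 is the only language question.
- Appendix 7, as far as its text can be read: no language field.
- Section 5.4: the ICES data are named as the source for socioeconomic status and education, not for language.

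No named source separates patients with a barrier that did not hinder from patients with no barrier.

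**Step 2. Where each patient is coded.**

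| Patient | Planned subgroup | Item 5 |
|---|---|---|
| No barrier | Not present | No |
| Barrier, did not hinder | Present | No |
| Barrier, hindered | Present | Yes |

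The middle row is misplaced.

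**Step 3. Size, by illustration.** Inputs:
- Immobilization under usual care is 100% in every group (section 3.6: "assuming a control arm proportion of 100" per cent).
- e_nh = 60 points avoided when a barrier does not hinder, and the same with no barrier. This is an assumption. The pilot figure in section 2.1 is about 60%, but it is an overall figure.
- e_h = points avoided when a barrier hinders. Assumed 0, 20, 40 or 60.
- h = share of barriers that hinder. Assumed 25%, 50% or 75%.

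Formulas:
- effect in all barrier patients = h × e_h + (1 − h) × e_nh
- effect in the form's Yes group = e_h
- understatement = (1 − h) × (e_nh − e_h)

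Example with e_h = 20 and h = 0.25: 0.25 × 20 + 0.75 × 60 = 50 points in all barrier patients, against 20 in the Yes group, so the understatement is 30 points.

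| e_h | Understatement, h = 25% | h = 50% | h = 75% |
|---|---|---|---|
| 0 | 45 | 30 | 15 |
| 20 | 30 | 20 | 10 |
| 40 | 15 | 10 | 5 |
| 60 | 0 | 0 | 0 |

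The subgroup contrast moves in the same way. With e_h = 20, barrier minus no barrier is −10, −20 or −30 points under the planned definition. Under the form it is 20 − 60 = −40 points whatever the value of h.

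**Step 4. Subgroup size.** If 5% to 10% of the 7,200 patients had a barrier (assumed), the planned subgroup would hold 7,200 × 0.05 = 360 to 7,200 × 0.10 = 720 patients. The Yes group would hold 7,200 × 0.05 × 0.25 = 90 to 7,200 × 0.10 × 0.75 = 540.

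**Step 5. Comparability across phases.** Under usual care every patient is to be immobilized whatever the rule says, so a paramedic may report hindrance differently before and after crossover. As an assumed example for comfort, let control proportions be 40% in hindered and 50% in non-hindered barrier patients, with a true gain of 10 points in both.
- If only 60% of the control-phase Yes group were truly hindered, its proportion is 0.6 × 40 + 0.4 × 50 = 44%, and the apparent gain is 50 − 44 = 6 points.
- If that dilution occurred in the intervention phase instead, its proportion is 0.6 × 50 + 0.4 × 60 = 54%, and the apparent gain is 54 − 40 = 14 points.

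This error can go either way. The documents do not show that it would occur.

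**The case against.** A reader might infer that the Yes group consists of patients in whom the rule failed or could not be applied, so that it must show little or no benefit. The documents do not support that. Hindered means made difficult. Such a patient can still be assessed and transported without immobilization. The decision to act on the rule is recorded separately in item 4, and actual immobilization in Appendix 7. Section 3.2 admits only patients able to follow commands. Age, mechanism, a simple rear-end collision and walking at the scene need little conversation. A fixed 60-point gap follows only from setting the benefit in hindered patients to zero, and nothing in the plan gives that value.

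The item is also asked during usual care, so hindered patients can formally be compared with hindered patients. This stands as an answer to a claim that no control comparison exists. It does not restore the missing barrier patients.

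It can further be argued that section 5.4 defines the subgroup by reference to the form, so the mismatch is one of labelling, and that difficulty in delivering the rule is itself a fair equity question. In part this stands: relabelling would make plan and form agree. But the stated question, whether people with a language barrier benefit differently, would remain unanswered. The study manual foreseen in section 5.3 may define the item more fully, but it is not among the documents, and the question printed on the form is the one paramedics answer.

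**Conclusion.** The concern holds in a limited form. The subgroup named in section 5.4 cannot be formed from item 5 or from any other named source. The group that can be formed is selected on a paramedic's perception of difficulty, given after the decision on the rule. The likely direction is an understated benefit for language-barrier patients and an exaggerated inequity. That direction rests on hindered patients gaining less than others, which is plausible but not documented.

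The size is unknown. Under the assumptions in the working it runs from 0 to 45 points on immobilization. It is zero if hindrance leaves the effect unchanged, and largest if hindered patients gain nothing and few barriers hinder.

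The importance is minor. One of six pre-specified subgroup factors is affected. The co-primary analyses, sample size, significance level and safety monitoring are not.

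**What to change.** Split item 5 in Appendix 6 into two questions:
- (a) *Was a language barrier present?* Place it before the section on the rule, so that it is answered before the rule is applied.
- (b) *If yes, did it hinder use of the rule?* Keep it where item 5 now stands.

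In section 5.4, define the subgroup by (a), and report (b) descriptively by study phase as a process measure. Both pieces of information are then kept.

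The cost is one extra field and a minor form revision through the Steering Committee and research ethics board (section 7.2), with a small change to the electronic form that is still to be developed with software vendors (section 3.7). Table 1 lists the trial as not yet recruiting, so no collected data would be affected.

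If the form cannot be changed, rename the subgroup in section 5.4 as patients in whom a language barrier was judged to hinder the rule. State there that it does not represent all patients with a barrier.

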3.4.2 Measures of Patient Benefit

- a) Proportion of patients feeling comfortable (score ≤4 on a 10-point Likert scale) (co-primary outcome of interest),
- b) Proportion of patients with a pain score ≤4 on a 10-point Likert scale upon arrival at the Emergency Department (ED),
- c) Time from EMS arrival to ED discharge or admission to hospital,
- d) Patient radiation exposure (in millisieverts) from diagnostic imaging of the spine,
- e) Number of skin pressure injuries, and
- f) Number of missed clinically important c-spine injuries. A clinically important c-spine injury includes any injury other than the following defined unimportant injuries which require neither specialized treatment nor follow-up: isolated avulsion fracture of osteophyte, isolated fracture of transverse process not involving the body or facet joint, isolated fracture of the spinous process not involving the lamina, isolated simple compression fracture <25% of body height.

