5.1 Data Collection Methods

Once training of paramedic staff has been completed, paramedics will begin evaluating eligible patients with the CCR. Each time an eligible patient is assessed using the CCR, the paramedic treating that patient will complete and submit an electronic CCR (see Appendix 6. Paramedic Data Collection Form). The paramedic will also record patient-reported comfort level and pain level on this form. Staff at the study coordinating centre will receive the electronic EMS-completed CCR, as well as a copy of the Paramedic Care Record (ePCR). Study staff will review the paramedic documentation in order to assess compliance with the study protocol and application of the CCR. Information on patient age, gender, mechanism of injury, field time, offload time and immobilization status are contained in the ePCR and will be recorded from there (see Appendix 7. Study Data Collection Form).

We will link the information obtained from paramedic care records to provincial administrative databases housed at ICES. This linkage will allow us to obtain information related to the initial ED visit, c-spine diagnostic imaging, hospitalization, and subsequent ED/clinic/family physician visits within 30 days of injury.

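### The co-primary comfort item asks for a comfort level on a scale where 10 is very uncomfortable, so some answers may be scored in the wrong direction; reword it before data collection starts

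*Combined protocol and SAP*

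**What the plan says.** Section 3.4.2 defines the outcome as "Proportion of patients feeling comfortable (score ≤4 on a 10-point Likert scale) (co-primary outcome of interest"). It prints no anchors, so the direction of the scale comes only from the form. Item 6 of Appendix 6 tells the paramedic to put two questions to the patient before handing over to the emergency department:

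- Item 6(i), pain: "On a scale of 1 – 10 (10 being the highest level of pain), how would you rate your pain right now".
- Item 6(ii), comfort: "On a scale of 1-10 (10 being very uncomfortable), how would you rate your comfort level right now".

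Section 5.1 confirms how the score is obtained: "The paramedic will also record patient-reported comfort level and pain level on this form". No other measurement of patient comfort is described. On power, Section 3.6 states that "we will have 90% power to detect a minimally important increase of 10% in the proportion of patients feeling comfortable", from an assumed control proportion of 50%, "using two-sided tests at the 2.5% level of significance".

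**The concern.** In item 6(ii) the noun and the anchor point in opposite directions. Asked for a comfort level out of 10, a patient who feels well may say 9 and be recorded as not comfortable. A patient in real discomfort may say 2 and be recorded as comfortable. The paramedic's own comfort question on the same form is less exposed, because its response categories are spelled out from very comfortable to very uncomfortable.

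The patients are acute trauma victims and include children from age 8. The form itself records language barriers. Age under 16 and language barrier are also pre-specified subgroups in Section 5.4. If misreading were more common in those groups, a smaller observed effect there could be mistaken for a real difference in benefit.

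At stake are the size of the estimated comfort effect and the power for one of the two co-primary outcomes. Power lost to misreading could be made up with more patients. Bias in the estimate could not.

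**Working it through.** **Inputs from Section 3.6:** difference 10 points, control proportion 50%, power 90%, two-sided alpha 0.025, ICC 0.05, 150 patients per service per three-month interval, 12 services over 4 intervals. Of the 12, 2 were added for unequal size and 2 for attrition, so 8 underlie the power figure.

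**Input not in the documents:** the reversal rate r. Values of 5% and 10% are assumptions chosen to show a range.

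**Step 1: reproduce the plan's figure.** I used the Hussey–Hughes variance (random service effect, fixed interval effects) and a normal approximation. The residual variance is 0.25, so the variance of a service-interval mean is 0.25/150 = 0.001667. The between-service variance is 0.25 × 0.05/0.95 = 0.01316. The critical value is 2.241.

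- 8 services split 2/4/2: SE 0.02865, power Φ(0.10/0.02865 − 2.241) = 89.4%.
- 8 services split 3/3/2: SE 0.02756, power 91.7%.
- 12 services split 4/4/4: SE 0.02216, power 98.8%.

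The stated 90% is therefore reproduced with about 8 services.

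**Step 2: effect of reversal on classification.** A reversed answer is 11 minus the true score. True scores of 1–4 become 10–7 and true scores of 7–10 become 4–1, so both cross the cut-off. True scores of 5 and 6 become 6 and 5 and stay not comfortable. With equal r in both conditions:

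observed difference = (1 − r) × change in P(score ≤ 4) + r × change in P(score ≥ 7)

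- If the 10-point gain comes entirely from patients who would have scored 7 or more, the second change is −10 points and the factor is (1 − 2r).
- If it comes entirely from patients who would have scored 5–6, the second change is 0 and the factor is (1 − r).
- Mixtures of the two fall in between.

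**Step 3: effect on power.** Starting from exactly 90%, difference/SE = 2.241 + 1.282 = 3.523, so power = Φ(3.523 × factor − 2.241). With 12 services, power = Φ(0.10 × factor/0.02216 − 2.241). The SE is held at its value without reversal.

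| r | Factor | Observed difference | Power from stated 90% | Power, 12 equal services |
|---|---|---|---|---|
| 0 | 1 | 10.0 | 90% | 98.8% |
| 5% | 1 − r = 0.95 | 9.5 | 87% | 98.0% |
| 5% | 1 − 2r = 0.90 | 9.0 | 82% | 96.6% |
| 10% | 1 − r = 0.90 | 9.0 | 82% | 96.6% |
| 10% | 1 − 2r = 0.80 | 8.0 | 72% | 91.5% |

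**Step 4: unequal reversal.** Suppose 20% score 5–6 in both conditions. The true distribution (≤4 / 5–6 / ≥7) is then 50/20/30 in control and 60/20/20 under the intervention.

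- Reversal 10% in control, none under intervention: control 0.9 × 50 + 0.1 × 30 = 48, intervention 60, difference 12.
- Reversal 10% in control, 20% under intervention: control 48, intervention 0.8 × 60 + 0.2 × 20 = 52, difference 4.

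The direction of bias is therefore not fixed.

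**The case against.** The strongest reply is that the form already guards against misreading. The anchor sits inside the question, ahead of the request for a rating. The pain item comes immediately before and also treats 10 as worst. A paramedic asks the question and can clarify an odd answer. Eligible patients have a Glasgow Coma Scale score of 15. Under Section 1.8.4 the Paramedic Committee helps develop and approve the forms. All of this stands and makes a high reversal rate less likely, but it does not make the rate zero.

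Second, if all 12 services stay, power remains at or above 90% up to r of about 11% even under the (1 − 2r) factor, ignoring unequal service sizes. That is correct. But Section 3.6 added those services for unequal size and attrition, and spare power does not remove bias: at r = 10% a true 10-point difference is still estimated as 8.0–9.0.

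Third, the form reached this review as text converted from a laid-out page, and a printed scale with end labels could have been lost. The missing label for 1 should be checked against the form itself. The mismatch between noun and anchor does not depend on it.

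A reader might go further and infer that reversed answers can never be detected. That is too strong. Pain is recorded at the same moment in the same direction, and Section 5.3 plans range and logic checks, so strong disagreement between the two scores could flag some records. Some disagreement will be genuine and no such check is specified, so reliable correction afterwards is not possible.

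**Conclusion.** The wording of a co-primary item is open to misreading, and that is worth fixing, but the frequency of misreading is unknown. Under equal reversal the loss is 0.5–1.0 points of a 10-point effect at r = 5% and 1.0–2.0 points at r = 10%. Power falls from 90% to about 82–87% and 72–82% respectively, and by much less if all 12 services are retained. These figures rest on the assumed r, on equal r in both conditions, and on the gain being drawn from scores of 5–6, from scores of 7 or more, or from a mixture of the two.

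Two stronger readings are tempting and not supported. One is that the form and the endpoint contradict each other: they do not, since low means comfortable in both. The other is that patients will be misclassified and the effect diluted as a matter of course. The documents give no evidence that any patient reverses the scale, nothing is lost at r = 0, and unequal reversal could enlarge the difference as well as shrink it.

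**What to change.** Before the first usual-care data are collected, reword item 6(ii) to ask about discomfort with both ends labelled, for example: *On a scale of 1 to 10, where 1 is completely comfortable and 10 is very uncomfortable, how uncomfortable are you right now?* Keep the definition of 4 or less in Section 3.4.2 and mention the direction of the scale in paramedic training. The analysis does not change.

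The cost is one changed line on the form and a sentence in training. Scores may be less directly comparable with any earlier use of the present wording. The timing is favourable: Section 1.2 lists the trial as not yet recruiting, and Figure 2 places the programming of the electronic form in the set-up year. A change made during the trial would be harder to handle, because in a stepped wedge the later intervals hold most of the intervention data.
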